5.5. Study visits

Baseline survey and randomization: All participants will undergo collection of contact information, a 30-minute baseline survey, and collection of blood spots for PEth and HIV viral load testing. After these activities, randomization will be conducted by the study coordinator (to keep the RAs blinded) using previously prepared sealed envelopes, in blocks of 9 to spread out the burden of the live boosters. Those randomized to Arms 1 or 2 will be referred to the study counselor for in-person counseling and training on the booster modes. Those randomized to Arm 3 will have no contact with the study counselor.

Six-month follow-up visit. Six months after baseline, we will conduct DBS collection and a quantitative survey, measuring alcohol consumption, and domain characteristics (Table 3).

Nine-month follow-up visit. Nine months after baseline, we will conduct DBS collection and a quantitative survey, measuring alcohol consumption, intervention usability and satisfaction, social desirability, and domain characteristics (Table 3). After data and specimen collection, those in the control arm will be offered the intervention, and will be allowed to choose their preferred method of booster delivery. We will also conduct **IDIs** with 8-12 participants per study arm. These participants will be selected using the a priori categories, with roughly equal numbers of those receiving boosters by SMS and by IVR within Arm 2. The aim of the IDIs will be to explore acceptability and experiences with all three study arms, including the two modes of tech delivery. These interviews will be coded and analyzed using the methods described below (statistical analysis plan).

Individual in-depth interviews at 3-6 months: Following participation in the intervention phase of the trial, a select number of participants (8-12 per study arm) will be invited to participate in a follow-up one-on-one, semi-structured qualitative interview with a research assistant. One third of these participants will participate in the qualitative interview

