Literacy, cell phone use	X			Ability to read this sentence when shown ("Please read this sentence out loud"), hours phone turned on and charged, SMS use, phone sharing
Alcohol use	X	X	X	AUDIT-C, drinking patterns, beverage-specific typical and maximum drinking, ¹³⁸ 3 week timeline follow-back ¹³⁹
Psychosocial variables/scales	X		X	Social support, ¹⁴⁰ HIV stigma, ¹⁴¹ Center for Epidemiologic Studies Depression Scale (16 items), ¹⁴² Stages of Change Treatment Eagerness Scale (19 items), ¹⁴³ Marlowe Crowne Social Desirability Scale (11 items, baseline and follow-up) ¹⁴⁴
Intervention characteristics			X	Client Satisfaction Scale-8 (8 items) ¹⁴⁵ , System Usability Scale (10 items) ^{146,147} Perceived Awareness of the Research Hypothesis Scale (demand characteristics; 4 items) ¹⁴⁸

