5.6. Specimen collection and laboratory procedures

DBS collection and testing. DBS collection will occur at the baseline, 6-month, and 9-month study visits. Six 50 µl drops of blood will be collected onto two Whatman 903 filter papers (3 spots each), which will be allowed to dry for ≥24 hours, and then stored packaged with a desiccant in a -80C freezer at the MUST laboratory.¹²⁷

Viral suppression: Plasma HIV viral load will be measured at baseline and 9 months using the Cepheid Xpert HIV-1 RNA assay, run on an existing GeneXpert platform in Mbarara, Uganda, that has been in use for our ongoing trials.

PEth levels: The DBS card will be tested for PEth level at the United States Drug Testing Laboratories using liquid chromatography-tandem mass spectrometry (LC/MS/MS) as described.¹²⁹ We will obtain a Materials Transfer Agreement to ship the DBS to the U.S.; no laboratories in Africa conduct this test.

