5.7. Measurements

5.7.1. Outcome variables

Efficacy analyses Outcome variables The primary outcome variable will be the number of days drinking (prior 3 weeks, TLFB) at 6 and 9 months. We chose this variable because (a) days drinking was the main outcome in the HWHL trial,¹⁶ (b) of several self-reported drinking variables, the number of drinking days was most highly correlated (Spearman $r=0.74$) with PEth level in a validation study in Uganda,⁹⁵ and (c) this variable may also be the least susceptible to bias because it does not require reporting the number of drinks, which can be challenging where non-standard drinks are common.⁹ We will use PEth level as an objective measure of prior 21-day alcohol use to confirm the findings obtained using self-report. Another main outcome variable will be HIV viral suppression at 9 months. Secondary outcomes will include the AUDIT-C score, which was associated with increased mortality in HIV-infected drinkers,¹³ and the number of heavy drinking days ($\geq 4/5$ drinks per occasion by females/males, respectively), the standard measure for pharmacotherapy trials. Other exploratory outcomes will include CD4 cell count and ART adherence.

Booster uptake and satisfaction Outcome variables Tech booster uptake will be measured from data extracted from the technology databases that record the SMS and IVR interactions. Uptake will be the proportion of sessions in which the participant answered all the questions prior to the final sign-off message; the denominator for this will be the number of tech booster sessions initiated by the system. Live booster call uptake will be tabulated from the counselor's call record forms that will be entered weekly into the study database. We will also determine the proportion of participants who request a counselor call back. We will also calculate intervention satisfaction in each arm using the Client Satisfaction Scale-8.¹⁴⁵ Among those in the tech booster arm (Arm 2), we will calculate usability via the System Usability Scale, used to evaluate new technology,^{146,147} and the proportions that chose SMS over IVR, overall and by reading literacy (yes/no).

Independent variables The predictor variable will be study arm by month (6 or 9 months).

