5.9.1. Primary analyses

Efficacy analyses

The analysis for primary outcome variable 1 (alcohol reduction) will measure the number of drinking days (of the prior 21) at six months and nine months, in pairwise comparisons of the study arms, controlling for baseline days drinking (of the prior 21).¹⁴⁹ The analyses will be conducted as intention-to-treat, and we will use Poisson or negative binomial regression for the count data, i.e. the number of drinking days at 6 and 9 months, controlling for baseline days drinking. The PEth level will be transformed to log10 PEth before analyses, based on PEth's highly skewed distribution and we will use linear regression for this outcome.

The analysis for primary outcome variable 2 (HIV viral suppression) will use logistic regression to compare the proportions with viral load<500 copies/ml, controlling for baseline viral load. We will adjust these analyses for baseline characteristics that exhibit imbalance between groups (based on a p-value ≤ 0.1 in comparisons of potential confounders listed in Table 3).

Secondary outcomes: Other exploratory outcomes will include CD4 cell count and ART adherence.

Missing data We will evaluate differences in baseline characteristics between those lost to follow-up versus those who are retained.¹⁵² If it is reasonable to assume that data are missing at random, multiple imputation methods will be applied to account for the missing data.^{152,153} We will also consider pattern mixture models,¹⁵⁴ which are applicable when the data are missing not at random.

Statistical power: With a sample size of 90 in each arm, assuming 90% 9-month retention, using a simplifying t-test for power calculations, we will have 80% power to detect a difference in the number of drinking days in the prior 21 between two study arms at nine months of ≥ 2.4 days, i.e. nearly 1 fewer day per week, as statistically significant ($\alpha=0.05$) assuming that the mean number of drinking days in the prior 21 in the control group is 7 (standard deviation is 5.5, based on prior data). Given that this is a pilot study we will not adjust for multiple comparisons.

Booster uptake and satisfaction analyses

Analyses We will calculate 95% confidence intervals for the outcomes listed above. We will conduct preliminary tests of whether the mean completion proportions and satisfaction scores differ by booster arm (live versus tech) by conducting 2-sample tests (t-test or Mann-Whitney).

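### The log10 PEth regression names no baseline PEth covariate, although the specimen is taken before randomization; the value used for undetectable PEth is also unstated

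*Combined protocol and SAP*

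**What the plan says.** Section 5.9.1 sets out three efficacy models.

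- Drinking days at 6 and 9 months: Poisson or negative binomial regression, adjusted for baseline drinking days.
- Viral suppression: logistic regression, "controlling for baseline viral load".
- PEth: "The PEth level will be transformed to log10 PEth before analyses", and "we will use linear regression for this outcome". No covariate is named.

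Further adjustment is limited to characteristics imbalanced at p ≤ 0.1 in "comparisons of potential confounders listed in Table 3". The alcohol row of Table 3 lists "AUDIT-C, drinking patterns, beverage-specific typical and maximum drinking" and a three-week timeline follow-back. All of these are self-report; PEth is not listed.

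The baseline measurement exists. Section 5.5 includes "collection of blood spots for PEth and HIV viral load testing" among the activities completed before randomization, and Section 5.6 says "DBS collection will occur at the baseline, 6-month, and 9-month study visits".

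On the role of PEth, Section 5.7.1 says "We will use PEth level as an objective measure of prior 21-day alcohol use to confirm the findings". Section 5.9.2 treats self-report and PEth as conclusive when they agree on statistical significance, and turns to social desirability and demand scores when they do not. The documents state neither a PEth assay limit nor a value for results below it.

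**The concern.** PEth is the only one of the three outcomes whose own baseline is not named as a covariate. A participant's baseline PEth is likely to be among the better predictors of later PEth, so leaving it out puts explainable between-person variation into the residual. The reference cited for adjusting drinking days (149) is, by its title, about baseline adjustment of continuous outcomes, and log10 PEth is the alcohol outcome analysed by linear regression.

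At stake is precision, not bias. PEth is the safeguard against under-reporting, and its significance enters the concordance rule. If the intervention truly lowers PEth, an avoidably imprecise test is more likely to miss it, which sends a significant self-report result to the softer reading of social desirability and demand scores.

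The second, smaller issue is the undetectable result. Section 3 says PEth forms only when alcohol is present, and the intervention aims to reduce drinking. Eligibility looks back 3 months while PEth reflects about 3 weeks. Results at or below the assay limit are therefore plausible at every visit, and the log of zero does not exist.

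**Working it through.** **Inputs from the documents.** 90 per arm, 90% retention at 9 months, SD 5.5 days, detectable difference 2.4 days, 80% power, alpha 0.05 (Section 5.9.1). Spearman correlation of drinking days with PEth is 0.74 in a validation study (Section 5.7.1). **Assumed:** a two-sided test, and a baseline-to-follow-up correlation r of log10 PEth between 0.4 and 0.7.

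**Step 1. Reproduce the plan's figure.** Analysed per arm: 90 × 0.9 = 81. Power for 2.4 days with SD 5.5 is 79.3% (normal) or 78.8% (noncentral t), against the stated 80%. The difference detectable with exactly 80% power is 0.443 SD by the t calculation, and 0.443 × 5.5 = 2.44 days. The plan's figure is reproduced. It gives no power figure for PEth, so 0.443 SD serves as the unadjusted reference.

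**Step 2. No baseline alcohol covariate in the PEth model.** Adding baseline log10 PEth multiplies the residual variance by 1 − r² and the interval width by √(1 − r²). Equivalent sample size is 81/(1 − r²).

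| r | Variance cut | CI narrower | Detectable difference | Power at the unadjusted 80% effect | Equivalent n per arm |
|---|---|---|---|---|---|
| 0.4 | 16% | 8% | 0.406 SD | 86% | 96 |
| 0.5 | 25% | 13% | 0.384 SD | 90% | 108 |
| 0.6 | 36% | 20% | 0.354 SD | 94% | 127 |
| 0.7 | 49% | 29% | 0.316 SD | 98% | 159 |

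The power column uses the normal approximation. Simulation of 4,000 trials gave 80% without and 90% with the covariate at r = 0.5, and 80% and 97% at r = 0.7.

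**Step 3. Baseline drinking days already in the PEth model.** Let ρ = 0.74 be the correlation of baseline days with baseline PEth (the Spearman value, used as an approximation), and c the correlation of baseline days with follow-up PEth. Then

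R² = (r² + c² − 2rcρ)/(1 − ρ²), and variance cut = 1 − (1 − R²)/(1 − c²).

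- Largest gain, r = 0.7 and c = 0.74 × 0.7 = 0.518: R² = (0.490 + 0.268 − 0.537)/0.4524 = 0.490. Cut = 1 − 0.510/0.732 = 0.303. The CI is 16.5% narrower, equivalent to 81/0.697 = 116 per arm.
- Smallest gain, r = c = 0.4: R² = (0.16 + 0.16 − 0.2368)/0.4524 = 0.184. Cut = 1 − 0.816/0.840 = 0.028. The CI is 1.4% narrower, equivalent to 83 per arm.

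Varying ρ from 0.6 to 0.8, the range Section 3 gives for PEth against consumption, widens the gain to 1.1-21.3%.

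**Step 4. Value for undetectable PEth (illustrative).** Assume 10% of controls and 20% of an intervention arm undetectable, a detectable control mean of 2.0 log10, detectable intervention values 0.15 lower (1.85), and SD 0.6. With v = log10 of the substituted value,

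difference = (0.2v + 0.8 × 1.85) − (0.1v + 0.9 × 2.0) = 0.1v − 0.32.

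| Substituted (ng/ml) | Difference (log10) | Geometric mean lower by | Chance of p < 0.05 (simulated) |
|---|---|---|---|
| 1 | −0.32 | 52% | 65% |
| 2 | −0.29 | 49% | 64% |
| 4 | −0.26 | 45% | 63% |
| 10 | −0.22 | 40% | 59% |

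If undetectable results were dropped, the difference would be −0.15 and the chance of p < 0.05 about 29%.

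**The case against.** The best reply is that baseline adjustment was probably intended. The PEth sentence stands in a paragraph that opens with baseline adjustment, both neighbouring models have it, and the cited reference is about it. That is plausible. But the only baseline the paragraph names is drinking days, so this reading puts days, not PEth, into the model, and Step 3 shows a gain remains.

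The size is also uncertain. The correlation is assumed, and enrolling only AUDIT-C positive participants may narrow the baseline range and lower it. With baseline days already in the model, the low end is negligible. This stands, and it is why a range is given.

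The concordance rule also counts two non-significant results as conclusive, so a sharper PEth test could break a concordant null. This is true. However, adjustment does not raise the false-positive rate when there is no PEth effect. Where a real effect exists, finding it is the purpose of the measurement. The net effect on the rule was not computed.

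The point about undetectable values is weaker. The 40-52% spread compares substitutes tenfold apart. Halving the substitute moves the difference by only 0.03 log10 per 10-point gap in the proportion undetectable. With the assumed mean and SD, some detectable values would fall below 10 ng/ml, so that case is extreme. The assay reference may state a limit, and nothing in the plan says such results would be dropped. As missing detail alone this would not justify a comment; it belongs with the covariate change because it concerns the same sentence.

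Finally, PEth supports the primary outcome in a pilot. That limits the weight of the point but does not argue against an inexpensive improvement.

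**Conclusion.** The concern holds. As written, the PEth model omits the baseline value of its own outcome, and no other rule in the plan brings it in. The treatment comparison is unbiased; the cost is precision.

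For an assumed correlation of 0.4 to 0.7, the interval would be 8-29% narrower than with no baseline alcohol covariate, and about 1-17% narrower than with baseline drinking days alone (the latter taking the 0.74 correlation to hold at baseline). The documents do not fix where in these ranges the trial would fall.

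The unstated value for undetectable PEth is secondary. Under the illustrative assumptions it changes the effect size handed to the future trial more than it changes significance. Excluding those results would matter much more. The sponsor should make both changes before analysis; neither gap invalidates the trial.

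**What to change.** In Section 5.9.1, add baseline log10 PEth as a covariate in the 6- and 9-month PEth regressions. In the same place, state the assay limit and one value to be used for results below it, at baseline and at follow-up alike. Say that an undetectable result is an observed result and is neither dropped nor imputed as missing. Repeating the analysis with a second value is an optional sensitivity analysis.

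The cost is SAP wording only: the specimens, assays and visits are already planned. A simple rule is needed for participants without a baseline PEth result, and the estimate will keep some dependence on the value chosen for undetectable results.

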5.9.2. Additional analyses

Exploratory analyses will examine the exposure to the boosters, in an as-treated analysis. For example, within the tech arm, we may examine whether the number of completed booster sessions is associated with the number drinking days in the prior 21, at six and nine months. Because these are non-randomized exposures, we will explore using propensity score analyses¹⁵⁰ to attempt to balance the groups. We will also examine effect moderation by variables found to impact intervention efficacy, such as gender and depression¹⁵¹ and by literacy.

PEth versus self-report We will consider findings that are concordant by self-report and PEth (i.e. both analyses statistically significant or both not reaching statistical significance) to be conclusive. If the findings are discordant, we will examine the pattern of SDS scores and demand characteristics (Table 3). We found in our previous studies that, after controlling for PEth level, adjusted SDS means were 0.88 points lower ($p<0.01$) for those reporting versus those denying recent unhealthy alcohol use, while PEth levels were not associated with SDS ($p=0.28$, unpublished analyses). We will conclude in favor of the PEth results if the patterns are consistent with under-report (i.e. associations of higher SDS and demand scores with lower self-reported alcohol use at the same PEth level, suggesting under-reporting).

Missing data We will evaluate differences in baseline characteristics between those lost to follow-up versus those who are retained.¹⁵² If it is reasonable to assume that data are missing at random, multiple imputation methods will be applied to account for the missing data.^{152,153} We will also consider pattern mixture models,¹⁵⁴ which are applicable when the data are missing not at random.

6. Safety considerations

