Alcohol use has a high impact on HIV transmission and outcomes. Alcohol use has been consistently associated with reduced ART adherence,¹⁰ with the odds of missing a dose increasing with each drink.^{32,33} In a longitudinal study of 438 persons at the Immune Suppression Syndrome (ISS) HIV Clinic in Mbarara, Uganda (our proposed study site), unhealthy alcohol use (AUDIT-C score for women: ≥ 3 , for men: ≥ 4) was the strongest independent predictor of <90% adherence (adjusted odd ratio [AOR] 2.56; 95% confidence interval [CI]: 1.41-4.66) and incomplete viral suppression (AOR: 2.51, 95% CI: 1.69–3.72).¹¹ Alcohol use has repeatedly been associated with increased sexual risk behavior and HIV transmission.³⁴⁻⁴⁰ Approximately 25% of persons with HIV worldwide are unhealthy drinkers.⁴¹⁻⁴⁷ Thus, unhealthy alcohol use is a significant barrier to suppressing HIV, and reducing unhealthy drinking is consistent with NIH HIV priorities.

Multi-session in-person alcohol interventions are efficacious but not scalable. Counseling interventions to reduce alcohol consumption from risky levels before more severe consequences occur have shown efficacy to reduce drinking by 15-30% one-year post intervention,^{5,48-55} and multi-session interventions have the strongest evidence of an effect on alcohol consumption.⁵ In the few alcohol intervention trials conducted in SSA, the most consistent evidence for alcohol intervention efficacy was for interventions delivered over 4-6 in-person sessions,^{17,21,22} as compared to those with one session,^{23,24} or one session followed by a booster call.²⁵ Multi-session alcohol interventions for those with HIV conducted worldwide have been successful at reducing alcohol use,^{15-18,22} with only a few exceptions.^{19,20} Yet multi-session interventions with several in-person visits are unlikely to be scalable or cost-effective in SSA.⁸

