Comparison of live versus automated booster calls. There are several strengths and limitations to consider for live versus automated interventions, including issues of network quality, message length, confidentiality, and literacy requirements (Table 2). While overall, analyses suggest that interventions with live counselors have better results than technology delivered interventions,⁷⁷⁻⁸⁰ it is not known how these modes of delivery compare for booster session delivery. There is high enthusiasm for technology-based interventions⁸¹ and several studies using SMS or IVR for improving ART adherence in SSA have been quite successful.^{82,83} Advantages to 2-way automated messaging (SMS or IVR) include flexibility in the timing of the messages, standardization, and low cost, while disadvantages include the limited ability to personalize and, for SMS, literacy (Table 2). Live boosters allow for a more personal experience but have high counselor time and cost, may depend on phone network quality, and have low flexibility in timing for the calls. Thus we feel that there is considerable equipoise between the methods and impetus to explore both tech and live booster calls, and gather preliminary data on the uptake, acceptability, effectiveness, and cost of these methods.

Cost estimates for mobile technology interventions in SSA are scarce. Few studies have examined the costs associated with mobile phone-based interventions,^{28,61} via live or tech delivery, although screening and brief interventions have been shown to be cost effective in the primary care setting in the US.^{48,84,85} The preliminary cost data will guide short-term decisions on which interventions to include in a future larger trial, while long-term implementation decisions will also ultimately depend on cost.⁸

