5.9. Statistical analysis plan

The analyses below will provide effect sizes to inform a future large-scale trial.

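### The plan calls agreement between self-report and PEth conclusive even when neither is significant, but at this sample size two non-significant results cannot exclude a worthwhile reduction in drinking

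*Combined protocol and SAP*

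**What the plan says.** Section 5.9.2 (PEth versus self-report) sets the rule for combining the two alcohol measures. Findings are concordant when they are "both analyses statistically significant or both not reaching statistical significance) to be conclusive". When they are discordant, social desirability (SDS) and demand scores are examined: "We will conclude in favor of the PEth results if the patterns are consistent with under-report".

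The rule acts on the efficacy analyses of Section 5.9.1, which are made "in pairwise comparisons of the study arms". It therefore covers each intervention arm against standard of care and also live against tech boosters. Section 5.7.1 gives PEth the role of an objective measure "to confirm the findings obtained using self-report".

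Section 5.9 states the purpose: "The analyses below will provide effect sizes to inform a future large-scale trial". Section 5.9.1 calls the study a pilot and powers it for a difference of 2.4 drinking days. The background in Section 3 says that counseling interventions "have shown efficacy to reduce drinking by 15-30% one-year post intervention".

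**The concern.** The rule makes significance status the only test of whether a finding is conclusive. A double non-significant result qualifies however wide the intervals are. As worded, so would two significant results pointing in opposite directions.

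Non-significance in a pilot is weak evidence of no effect, and a second non-significant test does not repair that. PEth comes from the same participants, and Section 5.7.1 reports a Spearman correlation of 0.74 with drinking days, so the two tests are not independent evidence.

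What is at stake is the description of the results. A study meant to hand effect sizes to a larger trial could report as settled a comparison whose interval includes effects of the size the background expects. This applies to live versus tech as well, where the true difference may be smaller than either arm's difference from control.

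A lesser point: the rule for discordant results names no comparison by arm. Under-reporting of equal size in both arms could satisfy it without explaining a difference between arms.

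**Working it through.** **Inputs.** From Section 5.9.1: 90 per arm with 90% retention gives 81; the mean "in the control group is 7 (standard deviation is 5.5, based on prior data"); alpha 0.05, taken as two-sided; baseline drinking days as a covariate. From Section 3: a 15-30% reduction, which on 7 days is 1.05 to 2.10 days. Applying that range, stated for drinking at one year, to drinking days at nine months is an assumption. The documents do not give the baseline-outcome correlation (rho) or any SD or effect for log10 PEth.

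**The plan's own figure.** SE = 5.5 × √(2/81) = 0.864 days. Power for 2.4 days = Φ(2.4/0.864 − 1.96) = Φ(0.82) = 79% (78.8% with the t distribution). The stated 80% is reproduced. Note that 2.4/7 = 34%, above the whole 15-30% range.

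**Width of the interval.** In days: 1.96 × 0.864 = 1.69, about 1.7. On the ratio scale, with the same coefficient of variation in both arms, SE(log ratio) = √(2 × (5.5/7)²/81) = 0.1235, or 0.1235 × √(1 − 0.25) = 0.1069 if rho = 0.5.

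| Observed ratio | 95% CI, unadjusted | 95% CI, rho = 0.5 (assumed) |
|---|---|---|
| 1.00 | 0.79 to 1.27 | 0.81 to 1.23 |
| 0.82 | 0.64 to 1.04 | 0.66 to 1.01 |

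**Observed ratio 1.00.** Neither interval excludes 0.85. Excluding it unadjusted would need 2 × (5.5/7)² × (1.96/ln(1/0.85))² ≈ 180 retained per arm; with rho = 0.5, × 0.75 ≈ 135. With 81 per arm it would need 1.96 × 0.1235 × √(1 − rho²) < ln(1/0.85) = 0.1625, that is, rho above about 0.74.

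**Observed 18% reduction (my illustration).** In days: 0.18 × 7 = 1.26, p = 0.147, 95% CI −0.45 to 2.97 days, or −6.4% to 42.4% of 7. A negative binomial model with dispersion (5.5² − 7)/7² = 0.474 gives p = 0.112 and −4.8% to 35.8%. Each interval covers all of 15-30%. Significance is reached once rho exceeds about 0.57 on the log-ratio scale or about 0.67 on the day scale. An uncorrected Poisson model would give p = 0.0015, but the variance is 5.5²/7 = 4.3 times the mean, so its standard error would be too small.

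**Chance of a double null (illustration only).** Take two normal test statistics with means δ/0.864 for self-report and f × δ/0.864 for PEth, where f is PEth's standardized effect relative to self-report, and with correlation 0.5 to 0.8 between the tests. The probability that both lie within ±1.96, unadjusted, is about:

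| f (assumed) | δ = 1.05 days | δ = 2.1 days |
|---|---|---|
| 0.5 | 73-75% | 30-32% |
| 1.0 | 65-69% | 17-23% |
| 1.5 | 49-53% | 3-5% |

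The overall range is 49-75% for 1.05 days and 3-32% for 2.1 days.

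**The case against.** The best defence is a narrower reading. The sentence contrasts concordant with discordant findings, and only discordance triggers the under-reporting review. Conclusive might then mean just that no adjudication between the measures is needed. This does not quite work: concordant already says that the measures agree, and the paragraph goes on to state what the trial will conclude. But the reading is possible, which is a reason to change the word.

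Several other objections stand:

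- Requiring two nulls is stricter than relying on self-report alone, which would be non-significant in about 77% of trials at 1.05 days and 32% at 2.1 days. The rates above mainly reflect pilot power.
- No single double-null rate can be fixed from the documents, because nothing is given for log10 PEth. Only the range is defensible.
- The 18% example depends on a baseline correlation that the documents do not state.
- Favouring a biomarker where under-reporting is known is reasoned in Section 3. The discordance rule is worded as a judgement on a pattern. A reader might take it for an automatic selector, but the text does not say so.

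A reader might also infer that a null for live versus tech would be declared equivalence and that cost would then decide, since Section 3 says "The preliminary cost data will guide short-term decisions on which interventions to include in a future larger trial". That sentence does not mention this rule, and no section claims equivalence.

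**Conclusion.** The rule is wrong as written: agreement in non-significance is not a conclusive finding without a condition on the intervals. On the plan's inputs, even identical observed means leave a 15% reduction open, both unadjusted and at an assumed baseline correlation of 0.5; the correlation would have to exceed about 0.74 to change this. An observed 18% reduction is non-significant, with an interval covering 15-30%, when unadjusted or with a correlation up to about 0.57 to 0.67, depending on the scale.

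The reach is limited. The documents tie no go/no-go decision to the rule, so it does not follow that the trial would discard an effective intervention. The missing comparison by arm in the discordance rule is a secondary gap, and its size cannot be judged from the documents.

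**What to change.** In Section 5.9.2:

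1. Replace conclusive with concordant, and report both arm effects with 95% CIs for every pairwise comparison.
2. Call an effect supported only when both results are significant in the same direction.
3. Describe a double non-significant result as inconclusive unless the CIs exclude a smallest effect of interest fixed before analysis: a rate ratio for drinking days and a mean difference for log10 PEth, applied in both directions for live versus tech.
4. When results are discordant, report both estimates with CIs. Also compare SDS and demand scores by arm at 9 months, when Table 3 schedules both, and treat this as supporting evidence.

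The cost is SAP wording, a choice of margins (the documents offer no basis for the PEth one) and one comparison of data already collected. More results will be labelled inconclusive. If the true ratio is 1.00, the drinking-days CI excludes 0.85 in Φ(0.1625/0.1235 − 1.96) = 26% of trials and 0.70 in Φ(0.3567/0.1235 − 1.96) = 82% (33% and 92% at rho = 0.5). Requiring PEth as well lowers these figures. A null against the larger margin can still be shown.
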